**Table 1. Study Schedule of Assessment**

Visit Identifier' Abbreviations used in this table may be found in Section 10.11 .	Screening	Baseline (Day 1)	Day 5	Day 10	Day 15	Day 21	Day 28	Day 35	Day 44	LTF/U		ET (pilot to Day 44)	Notes
										Week 12	Week 24		
Visit Window	Day -1 to Day 1	0 days	bl:1 day	bl:1 day	±2 days	±2 days	±2 days	±3 days	±3 days	±1 days	±7 days	±5 days	
 
Screening procedures may be done from Day -1 to Day 1, and may be completed on the same calendar day as Baseline/Day 1 procedures. If screening and baseline visits are conducted on the same calendar day, assessments and procedures that are listed to occur at both visits only need to be completed once.
 

Staff review of study intervention log,		Daily on Day 1 through Day 15											
 
See Section 6.5.
 

Record COVID-19-related medical visits			X	X	X	X	X	X	X	X	X	X	
 
COVID-19-related medical visits a participant has attended since the last assessment will be collected.
 
See Section 8.2.2.
 

Contraception check	X	X	X	X	X	X	X	X	X			X	
 
See Section 5.3.1, Section 8.1.4, and Annex 4.
 

Prior/concomitant medications	X	X	X	X	X	X	X	X	X			X	
 
All prescription and over-the-counter medications including vaccines taken by the participant within 30 days before study entry (considered prior treatment) will be recorded.
 
COVID 19-related vaccinations and monoclonal antibody or antiviral treatment for the treatment of COVID-19 at any time prior to the planned first dose will also be collected.
 
Concomitant therapies will be collected through the Day 44 visit or at ET visit.
 
See Section 6.9 and Section 8.1.4.
 

Adjunctive therapeutic procedures	X	X	X	X	X	X	X	X	X			X	
 
Will be collected through the Day 44 visit or at ET visit.
 

COVID-19 signs and symptoms		X	X	X	X	X	X	X	X	X	X	X	
 
See Section 8.2.5 and Appendix 10.
 

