5.3. Methods to Manage Missing Data

For SARS-CoV-2 RNA data, samples producing a result of <LLOQ or undetectable will not be considered missing, but rather will be imputed using values of 1.7 [log₁₀(50)] or 0.0 log₁₀ copies/mL, respectively. Missing SARS-CoV-2 RNA data will not be imputed.

As all analyses are descriptive, missing endpoint data will result in a summary where the N for that endpoint (and time point) is smaller than the total N of the corresponding analysis set. No imputation of the missing data will be performed.

For safety data, missing and partial dates will be programmatically handled according to Pfizer standards.

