6.2.8. Incidence of SAEs and AEs leading to discontinuations

The incidence of SAEs and AEs leading to discontinuation will be summarized by treatment group using the safety analysis set.

6.2.9. Proportion of participants with COVID-19-related hospitalization >24 hours, or death from any cause through Day 28

The proportion of participants with COVID-19-related hospitalization >24 hours, or death from any cause through Day 28 will be summarized. The cumulative proportion of participants hospitalized for the treatment of COVID-19 or death during the first 28 days of the study will be estimated for each treatment group using the Kaplan-Meier method to take account of losses to follow-up and summarized graphically for each treatment group.

For participants without an event who complete the Day 28 assessment, they will be censored at Day 28. For participants without an event who discontinue or are lost to follow-up before the Day 28 assessment, they will be censored at the last known date in the study.

6.2.10. Proportion of participants with death (all cause) through Week 24

The proportion of participants who died from any cause through Week 24 will be analyzed using the method specified in Section 6.2.9 and summarized for each treatment group. KM plots for each treatment group will also be provided. Participants without an event will be censored at the last known date in the study.

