6.2.13. Proportion of participants requiring invasive mechanical ventilation or ECMO

The proportion of participants requiring invasive mechanical ventilation or ECMO will be analyzed using the method specified in Section 6.2.9 and summarized by treatment arm through day 44 and through week 24. Participants without an event (at Day 44/Week 24) will be censored at that time or at the last known date in the study, whichever is later.

6.2.14. Number of days in hospital and ICU stay in participants with COVID-19-related hospitalization

The number of days of hospital stay and number of days of ICU stay in participants with COVID-19-related hospitalization will be summarized through Day 44 and through Week 24 by treatment group using descriptive statistics (ie, mean, median, range).

6.2.15. Number of COVID-19-related medical visits through Day 44 and through Week 24

The number of COVID-19-related medical visits through Day 44 and through Week 24 will be summarized by treatment group using descriptive statistics (ie, mean, median, range).

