Rebound in SARS- CoV-2 RNA up to Day 28 (NP) defined as a half \log_{10} copies/mL increase or greater relative to EOT (active) with follow-up viral RNA level \geq 3.0 \log_{10} copies/mL	Secondary	Evaluable with EOT (active) and 1 post-EOT not missing	No imputation for missing data	Descriptive (n, %)
Proportion with COVID-19-related hospitalization >24 hours, or death through Day 28	Secondary	Evaluable	Max censor time at Day 28	KM method
Proportion with death (all cause) through Week 24	Secondary	FAS	Max censor time at Week 24	KM method
Proportion with COVID-19-related hospitalization	Secondary	Evaluable	Max censor time at Day 44	KM method
Proportion with COVID-19-related ICU admission	Secondary	Evaluable	Max censor time at Day 44	KM method
Proportion requiring IMV or ECMO	Secondary	Evaluable	Max censor time at Day 44	KM method
Number of days in hospital and ICU stay	Secondary	Evaluable, participants with COVID- 19-related hospitalizat ion	In the absence of a specific record of a COVID-19-related hospitalization, participants will be considered to be out of hospital	Descriptive summary

DMB02-GSOP-RF02 7.0 Statistical Analysis Plan Template 31-Jan-2022 PFIZER CONFIDENTIAL TMF Doc ID: 98.03 Page 28 of 32

Endpoint	Analysis Type	Population	Data Inclusion and Rules for Handling Intercurrent Events and Missing Data	Analysis Model
Number of COVID- 19-related medical visits through Day 44 and through Week 24	Secondary	Evaluable	In the absence of a specific record of a COVID-19-related medical visit, participants will be considered to not have a COVID- 19-related medical visit.	Descriptive summary
Duration of each targeted COVID-19 signs/symptoms	Secondary	Evaluable	No imputation for missing data	KM method
Proportion with severe signs/symptoms attributed to COVID-19	Secondary	Evaluable	No imputation for missing data	Descriptive (n, %)

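### The COVID-19 medical-visit count scores time after withdrawal or loss to follow-up as visit-free, which lowers the mean and conflicts with SAP 5.3

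*SAP*

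**What the plan says.** SAP Appendix 1 gives the count its own rule for the Evaluable set: "In the absence of a specific record of a COVID-19-related medical visit, participants will be considered to not have a" COVID-19-related visit. The rule does not separate a participant who was asked and reported none from one who was never asked. SAP 6.2.15 adds only that the count through Day 44 and through Week 24 "will be summarized by treatment group using descriptive statistics (ie, mean, median, range"). It has no follow-up time, censoring, number observed or rule for death.

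SAP 5.3 says that "missing endpoint data will result in a summary where the N for that endpoint (and time point) is smaller than the total N" of the analysis set, and that "No imputation of the missing data will be performed". Nothing states which rule governs this endpoint.

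On data collection, the Protocol Schedule of Activities says that "COVID-19-related medical visits a participant has attended since the last assessment will be collected" at each visit from Day 5 to Week 24 and at early termination. Protocol 8.2.2 also places this collection at study visits. Under Protocol 7.3 an unreachable participant is treated as withdrawn. Under 7.2, withdrawing consent for future information ends data collection.

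The adjacent Appendix 1 row, days in hospital and ICU, has a similar rule: "In the absence of a specific record of a COVID-19-related hospitalization, participants will be considered to be out of hospital". That summary is limited to participants with a COVID-19-related hospitalization.

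**The concern.** After a participant leaves, nobody asks about visits, so no record can exist. Appendix 1 turns that silence into zero visits, and the raw mean divides by everyone. The more follow-up an arm loses, the lower its apparent use of care. Healthcare resource use is a stated secondary objective, so a reader could mistake a difference in retention for a difference in utilisation.

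The SAP guards against this elsewhere. SAP 6.2.9 estimates hospitalization or death through Day 28 "using the Kaplan-Meier method to take account of losses to follow-up", and 6.2.11 to 6.2.13 apply the same method to any hospitalization, ICU admission and ventilation or ECMO. The visit count has no counterpart. In addition, a programmer following 5.3 would drop incompletely observed participants from N, while one following Appendix 1 would keep them as zeros. The two tables would differ.

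**Working it through.** The plan gives no figure for this endpoint to reproduce: no expected visit rate and no loss rate. The check is therefore of direction and size under stated assumptions.

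**Inputs from the documents.** Week 24 is target Day 168 (SAP Appendix 2.1). There are about 50 participants per arm in the main population (SAP 2.4).

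**Assumptions.** A share d of an arm is lost, with loss times spread evenly over 168 days and unrelated to visits. Loss of 20% and 5% is used for illustration. Visits occur either at a constant rate or at an exponentially declining rate with time constant m = 15, 30 or 60 days, truncated at Day 168.

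**Step 1: share of visits lost under the zero rule.** A visit at time t goes unrecorded with probability d × t/168. The raw mean is therefore understated by d × E[t]/168, where E[t] is the mean visit time. For the declining rate, E[t] = m − 168·e^(−168/m)/(1 − e^(−168/m)).

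| Visit pattern | E[t]/168 | Understatement, d = 20% | Understatement, d = 5% |
|---|---|---|---|
| Declining, m = 15 | 0.0893 | 1.8% | 0.4% |
| Declining, m = 30 | 0.1749 | 3.5% | 0.9% |
| Declining, m = 60 | 0.2924 | 5.8% | 1.5% |
| Constant rate | 0.5 | 10% | 2.5% |

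The Day 44 count suffers less. At a constant rate, 20% loss over 168 days costs it 0.20 × (44/168)/2 = 2.6%.

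**Step 2: comparison of two identical arms, 20% versus 5% loss.** The ratio of raw means is (1 − 0.20·E[t]/168)/(1 − 0.05·E[t]/168). This is 0.99, 0.97 and 0.96 for m = 15, 30 and 60, and 0.900/0.975 = 0.92 at a constant rate. With equal loss the ratio is 1, although both means are too low.

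**Step 3: ascertainment between visits.** Step 1 assumes visits are captured up to the moment of loss. Early-termination visits apply only before Day 44, and later assessments are at Weeks 12 and 24 only. A participant lost after Day 44 therefore also loses the interval since the last completed assessment. On that basis, 20% loss understates the Week 24 mean by 2.0% (m = 15), 7.7% (m = 60) and 13.1% (constant rate).

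**Step 4: would a rate per participant-day repair it?** The arm's observed time is 1 − d/2 of the total. The rate relative to the truth is (1 − d·E[t]/168)/(1 − d/2). With d = 20%:

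- m = 15: 0.9821/0.9 = 1.091, an error of +9.1% (raw count −1.8%)
- m = 30: 0.9650/0.9 = 1.072, an error of +7.2% (raw count −3.5%)
- m = 60: 0.9415/0.9 = 1.046, an error of +4.6% (raw count −5.8%)

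The rate is right only when visits occur at a constant rate. With early clustering its error reverses sign, and at 15 and 30 days it is the larger of the two.

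**Step 5: mean cumulative count.** This sums, over observed visits, one divided by the number still under observation. In simulation with 20% uniform loss it recovered the true mean at m = 15, at m = 60 and at a constant rate, whether censored at loss or at the last completed assessment.

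**The case against.** The strongest case for leaving the plan alone is that the effect is small and visible. For an acute infection, early clustering of visits is at least as plausible as a constant rate over 24 weeks, and it brings the understatement down to a few percent. Nothing in the documents predicts unequal loss between blinded arms. SAP 6.4.2 already reports disposition and withdrawal reasons by arm, the early-termination visit recovers visits up to that point, and no hypothesis is tested. If visits averaged 0.5 per participant (assumed Poisson), the standard error of the log ratio between arms of 50 would be √(1/25 + 1/25) = 0.28, more than three times |ln 0.92| = 0.083. All of this stands and keeps the point minor. It does not remove the conflict with 5.3, or the fact that the rule scores unobserved time as zero use.

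A reader might also infer two stronger faults that the documents do not support:

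- **Death.** One might say the rule fills in time after death. Having no visits after death is fact, not imputation, and SAP 6.2.10 reports all-cause death by arm through Week 24. What is missing is a stated rule and deaths shown beside the count.
- **Hospital days.** One might say that row zero-fills all unobserved time. It covers only participants with a COVID-19-related hospitalization, so someone lost before any recorded admission adds no zero. Only loss after a recorded COVID-19 hospitalization matters.

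**Conclusion.** The point holds for the medical-visit count. Time after withdrawal or loss to follow-up is scored as visit-free, the mean is lowered, and an arm with more loss appears to use less care. Appendix 1 and SAP 5.3 give different instructions.

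At an assumed 20% uniform loss to Week 24, the understatement is about 2% to 6% if visits cluster early and 10% at a constant rate. It is somewhat more if visits since the last completed assessment are also lost. A reader might take the ratio of 0.92 between identical arms as the expected distortion. It is not: it needs both a constant rate and 20% versus 5% loss, and the documents give neither. With equal loss there is no distortion between arms.

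The endpoint is secondary and descriptive, and no test or primary conclusion is affected.

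**What to change.** In SAP 6.2.15 and the matching Appendix 1 row:

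1. Apply the no-record rule only to observed follow-up.
2. Estimate the mean cumulative number of visits per participant by arm at Day 44 and Week 24. Censor at withdrawal or the last completed assessment, and treat death as a terminal event after which no visits accrue, not as censoring.
3. Show the number observed to each time point, and report deaths beside the count.
4. Keep the raw mean, median and range as a supportive row.
5. State in SAP 5.3 or Appendix 1 which rule governs this endpoint, so that the two agree.

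A simple rate per participant-day should not be the main summary, because it errs in the opposite direction when visits cluster early.

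The cost is SAP wording, one derived follow-up-time variable and a slightly less familiar summary. No new data are needed.

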Appendix 2. Data Derivation Details

Appendix 2.1. Definition and Use of Visit Windows in Reporting

The following table defines the visit windows and labels to be used for reporting:

Visit Label	Target Day	Definition [Day window]
Baseline	1	Day -2 to Day 1
Day 5	5	Day 2 to Day 7
Day 10	10	Day 8 to Day 12
Day 15	15	Day 13 to Day 18
Day 21	21	Day 19 to Day 24
Day 28	28	Day 25 to Day 31
Day 35	35	Day 32 to Day 39
Day 44	44	Day 40 to Day 49
Week 12	84	Day 77 to Day 91
Week 24	168	Day 161 to Day 175

If multiple observations fall into the same window, choose the one closest to the visit and if equidistance, then choose the latter of the two. .

Abbreviation	Term
AE	adverse event
ANCOVA	analysis of covariance
BL	Baseline
BMI	body mass index
CaPS	CDISC aligned Pfizer Standards
CDISC	Clinical Data Interchange Standard Consortium
CI	confidence interval
COVID-19	coronavirus disease 2019
CRF	case report form
CSR	clinical study report
DMC	data monitoring committee
ECMO	extracorporeal membrane oxygenation
E-DMC	external data monitoring committee
eGFR	estimated glomerular filtration rate
FAS	full analysis set
ICU	intensive care unit
IMV	invasive mechanical ventilation
IRC	internal review committee
КМ	Kaplan-Meier
LLOQ	lower limit of quantitation
LS	least-squares
LSM	least-squares mean
MAR	missing at random
MedDRA	Medical Dictionary for Regulatory Activities
MMRM	mixed-effects model with repeated measures
MNAR	missing not at random
N/A	not applicable
NP	nasopharyngeal
PD	pharmacodynamic(s)
РК	pharmacokinetic(s)
РТ	preferred term
RAT	rapid antigen test
RNA	ribonucleic acid
RR	relative risk
SAE	serious adverse event
SAP	statistical analysis plan
SARS-CoV-2	severe acute respiratory syndrome coronavirus 2
SAS	safety analysis set
SD	standard deviation
SOC	system organ class
SOP	standard operating procedure

Appendix 3. List of Abbreviations

DMB02-GSOP-RF02 7.0 Statistical Analysis Plan Template 31-Jan-2022 PFIZER CONFIDENTIAL TMF Doc ID: 98.03 Page 31 of 32

Abbreviation	Term
TEAE	treatment emergent adverse event
ULN	upper limit of normal
US	United States
WHO	World Health Organization
WHODD	World Health Organization Drug Dictionary

DMB02-GSOP-RF02 7.0 Statistical Analysis Plan Template 31-Jan-2022 PFIZER CONFIDENTIAL TMF Doc ID: 98.03 Page 32 of 32
